We propose a single-center, double-blinded, placebo-controlled, randomized, Phase 2-3 clinical trial to test if hydroxychloroquine post exposure prophylaxis (hPEP) reduces the symptomatic secondary attack rate of COVID-19 among close contacts of known or suspected COVID-19 patients identified at the largest academic medical center in NYC and surrounding metropolitan area.

Setting: The study will be conducted in NYC, where the COVID-19 epidemic is rapidly accelerating. In order to optimize efficiency, the study will be initiated at the NYP/CUIMC campus in Washington Heights, with plans to expand across other NYP campuses if/as conditions allow. As this is a community-based study, where interaction is facilitated remotely, we wish to include the tri-state area as our immediate scope due to the patient demographic majority residing in this area.

Population: Currently asymptomatic adults (≥ 18 years old) meeting the following inclusion and exclusion criteria:

a. Inclusion criteria:

- a. Household contact of index case: currently residing in the same household as an index case:
 - i. Index case definition: individual evaluated at outpatient, emergency department (ED), or inpatient services who (1) tests positive for COVID-19, or (2) are defined as suspected cases, or persons under investigations (PUI), by the treating physician.
- b. Willing to take study drug as directed for 5 days.

b. Exclusion criteria:

- a. Age < 18 years old
- b. Suspected or confirmed current COVID-19, defined as: (1) temperature > 38 Celsius; (2) cough; (3) shortness of breath; (4) sore throat; or, if available (not required), (5) positive confirmatory testing for COVID-19
- c. Suspected or confirmed convalescent COVID-19, defined as any of the above symptoms within the prior 4 weeks.
- d. Inability to take medications orally
- e. Inability to provide written consent or eConsent
- f. Known sensitivity/allergy to hydroxychloroquine

- g. Current use of hydroxychloroquine for another indication
- h. Pregnancy
- i. Prior diagnosis of retinopathy
- j. Prior diagnosis of G6PD deficiency
- k. Major comorbidities increasing risk of study drug:
 - i. Hematologic malignancy
 - ii. Advanced (stage 4-5) chronic kidney disease or dialysis therapy
 - iii. Known history of ventricular arrhythmias
 - iv. Current use of drugs that prolong the QT interval (Table 1)

Table 1. Drugs that prolong QT, and for which current use will be an exclusion criterion for participation

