Study drug: the intervention will be a 5-day course of hydroxychloroquine sulfate (brand name, Plaquenil). Each participant will receive 12 tablets of hydroxychloroquine sulfate 200mg. They will be instructed to take two tablets (400mg) twice daily on day 1; for days 2-5, they will be instructed to take one tablet (200mg) twice daily. The rationale for this dosing regimen is as follows. A loading dose is important to efficacy, but loading doses >800mg/24 hours are expected to have a disadvantageous risk/benefit profile. The dose on the subsequent 4 days

(400mg/day) is within the standard long-term daily dosing range for autoimmune diseases. For comparison, other current trials of hPEP propose the following regimens:

- NCT04304053: 800mg on day 1, and 400mg on days 2, 3, 4. We believe that an additional day of therapy will be associated with minimal excess risk and the median incubation of CoV-SARS-2 is 5 days, suggesting that 5 days of prophylaxis may be superior to 4 days.
- NCT04308668: 800 mg orally once, followed in 6 to 8 hours by 600 mg, then 600mg once a day for 6 consecutive days. We believe that the loading dose and the follow-up doses are excessively high. Together with an extended (7-day) course of treatment, we believe that this regimen carries higher risk of adverse effects without clear benefit and with lower likelihood of regimen adherence.

Participants randomized to the placebo will receive an identical container of 12 placebo pills, with the same instructions for administration.

Follow up

Participant self-monitoring: participants will be asked to check and record their temperatures at home in the morning and in the evening. They will be instructed to contact the study if they develop a temperature >38 C, and/or if they develop cough or shortness of breath.

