Daily telephone or email follow-up: research personnel will contact participants by phone on a daily basis for 7 days post-randomization, and at 14 (+/- 3) and 30 days (+/- 3). They will conduct a structured interview to ascertain potential symptoms of COVID-19 (the primary outcome), adherence to and potential adverse effects of the study drug, and extent of ongoing exposure to the index case. Alternatively, if preferred by the participant, the participant will be able to submit answers to the daily symptomatic questionnaire via secure web-based questionnaire to support remote administration and immediate data capture. Participants with symptoms or signs of COVID-19 will be referred to the study physician, who will contact the participant and determine if he/she meets PUI criteria. The study physician will refer PUIs for confirmatory COVID-19 testing at NYP/CUIMC/WCMC.

Psychosocial Questionnaire at Day7: Resources for mental health and wellness are provided at the end of the psychosocial questionnaire for all participants, as well as instructions for seeking medical attention if participants experience significant distress or feel unsafe.

Participants who score in the severe or extremely severe range on the depression subscale, express passive or active suicidal ideation, or express thoughts of self-harm will be informed of mental health support hotlines, advised to seek care from a mental health professional, and encouraged to contact emergency services if they feel unsafe. For such participants who respond to the questionnaire online or by paper, an attempt will be made to contact them at the time the questionnaire is viewed to provide the information above.

Active surveillance of healthcare utilization: the research personnel will monitor study participants to determine if any participants present to the outpatient clinic or to the ED, and/or if they require hospitalization.

Extended follow-up of symptomatic participants: participants who develop COVID-19 symptoms will continue to be followed-up by daily telephone calls until 3 days following resolution of

symptoms in order to measure the duration of symptom (secondary endpoint).

Statistics

We plan a phase 2 study at NYP/CUIMC/WCMC, with the phase 2 as an internal pilot for a potential phase 3 study, which would be conducted across all NYP sites.

Population: Household contacts of COVID-19 cases with high-risk COVID-19 exposures

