Endpoint: Symptomatic, lab-confirmed COVID-19 over two-week follow-up, defined by:

1. COVID-19 infection confirmed within 14 days of enrollment, following self-report of COVID-19 symptoms to the research study.
2. COVID-19 infection confirmed within 14 days of enrollment, with self-report of COVID-19 symptoms to a treating physician.

Control outcome: The CDC has estimated symptomatic secondary attack rate of 10.5% (95% CI = 2.9%–31.4%) among household members of COVID-19 patients over 14 days (7) (<https://www.cdc.gov/mmwr/volumes/69/wr/mm6909e1.htm>).

Effect size: a 30% risk reduction from a 10.5% to 7.4% symptomatic secondary attack rate

Design:

- Placebo-controlled 1:1 randomized at NYP/CUIMC/WCMC
- Phase 2/3 internal pilot, with interim monitoring for futility and safety during the pilot phase
- Pilot phase: one-sided test at 10% significance; data obtained in pilot phase will be used to size the phase 3 trial, and the pilot data will be used in the final analysis at the end of phase 3
- Sample size for pilot phase: n = 800 per arm, i.e., total N = 1600

Secondary endpoints:

- Determination of symptoms consistent with PUI without confirmatory COVID-19 testing (e.g., if lost to follow-up)
- Duration, in days, of COVID-19 symptoms (cough, shortness of breath, and/or fever)
- Hospitalization for COVID-19
- Mechanical ventilation for COVID-19
- Mortality attributed to COVID-19

Additional notes on statistical design and analysis

This is a single-center, double-blinded, placebo-controlled, randomized internal pilot trial of a larger phase 2-3 seamless clinical trial. The trial objective is to evaluate if hydroxychloroquine post exposure prophylaxis (hPEP) given over a 2-week period will reduce symptomatic secondary attack rate of COVID-19 in household contacts of known or suspected COVID-19 patients. The study endpoint is symptomatic, lab-confirmed COVID-19 during the 2-week study period. In this pilot trial, we plan to randomize a total N=1600 participants to the treatment (hPEP) and the placebo in a 1:1 ratio, stratified by chromosomal sex and age group (<55 yo vs 55+).

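### Sore throat alone counts as suspected COVID-19 at entry but is missing from the follow-up self-report list and the duration endpoint, so some late-onset cases may not be confirmed in time

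*Combined protocol and SAP*

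**What the plan says.** All places are in the combined protocol and SAP.

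- **Entry (section 2, exclusion criterion b).** Suspected current COVID-19 is any one of "1) temperature > 38 Celsius; (2) cough; (3) shortness of breath; (4) sore throat; or, if available (not required), (5) positive confirmatory testing for COVID-19". Criterion c applies the same list to convalescent disease: "defined as any of the above symptoms within the prior 4 weeks".
- **Self-report in follow-up (section 2, Participant self-monitoring).** Participants are told to "contact the study if they develop a temperature >38 C, and/or if they develop cough or shortness of breath".
- **Scheduled contacts (section 2, Daily telephone or email follow-up).** These take place "on a daily basis for 7 days post-randomization, and at 14 (+/- 3) and 30 days (+/- 3" days. Each includes a "structured interview to ascertain potential symptoms of COVID-19 (the primary outcome"). The symptoms asked about are not listed there. Section 3a says only that the follow-up questionnaires cover respiratory and non-respiratory symptoms.
- **Route to a test (same paragraph).** Symptomatic participants go to the study physician, who is to "determine if he/she meets PUI criteria" and refers those who do for testing. The criteria are not itemised.
- **Primary endpoint (section 2, Statistics).** Infection confirmed within 14 days of enrollment, with COVID-19 symptoms reported either to the study or to a treating physician. The symptoms are not itemised.
- **Duration endpoint (Secondary endpoints).** "Duration, in days, of COVID-19 symptoms (cough, shortness of breath, and/or fever").

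**The concern.** A symptom that keeps a person out of the trial as a suspected case is not one that an enrolled participant is asked to report, and no reason is given. The primary event needs both symptoms and a positive test. The follow-up plan schedules no test for participants without symptoms, so within the study a test is reached only once a symptom is known. If a symptom is not volunteered and nobody asks about it, the case may not be confirmed inside the window.

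At stake is the event count behind the go/no-go decision. The pilot data also feed the phase 3 sample size re-estimation, so any under-ascertainment would carry forward. Separately, the duration endpoint gives no value to a confirmed case whose only symptom is sore throat.

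**Working it through.** **1. The lists side by side**

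| Place | Fever | Cough | Shortness of breath | Sore throat |
|---|---|---|---|---|
| Exclusion criteria b and c | yes | yes | yes | yes |
| Self-report instruction | yes | yes | yes | no |
| Duration endpoint | yes | yes | yes | no |
| Structured interview | not itemised | not itemised | not itemised | not itemised |
| PUI criteria | not itemised | not itemised | not itemised | not itemised |
| Primary endpoint symptoms | not itemised | not itemised | not itemised | not itemised |

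**2. When the difference matters**

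- Days 1 to 7: staff ask about symptoms daily, so sore throat can come to light whatever the participant volunteers. Whether a test follows depends on the unlisted PUI criteria.
- Day 8 to the next contact: that contact falls between day 14 - 3 = 11 and day 14 + 3 = 17. Until then the three-symptom instruction is the only study prompt.
- Confirmation must fall within 14 days. A call on day 11 leaves three days for a test and its result. A call on days 15 to 17 comes after the window has closed.

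The exposed group is therefore cases with onset after day 7, with sore throat but no fever, cough or shortness of breath in time, who neither volunteer it nor seek care.

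**3. The plan's own power figure**

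Inputs from section 2, Statistics: 800 per arm; one-sided Fisher's exact test with go if p < 0.10; placebo rate 10.5%; 30% reduction, so 0.105 x 0.70 = 0.0735. The plan prints 7.3% in two places and 7.4% in another, which are roundings of 7.35%. Summing the two binomial probabilities over all tables with p < 0.10 gives 80.2%. The stated 80% reproduces.

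**4. Effect of a loss**

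Let m be the share of all true events that are missed, equal in both arms. The observed rates become 0.105(1 - m) and 0.0735(1 - m). Their ratio stays 0.0735 / 0.105 = 0.70, so the relative risk does not move. Expected events with no loss are 800 x 0.105 = 84 on placebo and 800 x 0.0735 = 58.8 on drug.

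| m (assumed) | Placebo rate | Drug rate | Events lost, placebo / drug | Go probability (exact Fisher) |
|---|---|---|---|---|
| 0 | 10.50% | 7.35% | 0 / 0 | 80.2% |
| 1% | 10.40% | 7.28% | 0.8 / 0.6 | 79.8% |
| 3% | 10.19% | 7.13% | 2.5 / 1.8 | 79.1% |
| 5% | 9.98% | 6.98% | 4.2 / 2.9 | 78.4% |

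**5. What m means**

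m = (share of events that are sore throat only) x (share of those with onset after day 7) x (share of those not caught by another route). The documents give none of the three. As an illustration with assumed values, 10% x 30% x 100% = 3%.

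**The case against.** The strongest reply is that the self-report instruction is one route among several. The daily interviews cover non-respiratory as well as respiratory symptoms, and anyone with symptoms or signs goes to the study physician. Participants who become symptomatic continue with daily calls until three days after resolution, so onset by day 7 can carry daily contact beyond day 7. The study monitors clinic, ED and hospital visits, and the second limb of the primary endpoint counts symptoms reported to a treating physician. The lists may also differ on purpose: a broad screen at entry does a different job from a prompt to call.

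Most of this stands. It confines the problem to late onset and makes the likely loss small. It does not close the gap: surveillance and the treating-physician limb help only a participant who seeks care unprompted, and the plan gives no rationale for the difference. None of it touches the duration endpoint.

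A reader might infer several stronger things that the documents do not support:

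- *That sore-throat cases are never tested and are scored as non-events.* The interview items and PUI criteria are not listed, so sore throat cannot be said to be absent from them. No rule for missing outcomes is stated, so how an untested case would be scored is an inference.
- *That 10% or 20% of events could be lost.* The arithmetic gives 76.5% and 72.2%, but if 30% of events were late, a 20% loss would need 0.20 / 0.30 = 67% of them to be sore throat only and otherwise uncaught. Nothing supports that.
- *That the treatment effect is biased.* The trial is double-blind, and equal proportional loss leaves the relative risk at 0.70.

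**Conclusion.** The concern holds in a limited form. The symptom lists are inconsistent, and the symptom component of the primary endpoint is undefined. Following the stated rules, some cases with sore throat only and onset after day 7 may not be confirmed in time to count. A confirmed case of that kind has no defined duration, whenever its onset.

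The cost to the primary analysis is power, and it is small: 0.4, 1.1 and 1.8 percentage points for assumed losses of 1%, 3% and 5% of all events. These figures rest on three assumptions: equal loss in both arms, a 10.5% placebo rate that includes sore-throat-only cases (the cited source was not available to check), and values of m that the documents do not supply. The plan's 80% is correct as stated. The case for a change rests on having a defined endpoint at little cost, more than on the power lost.

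**What to change.** - Add sore throat to the Participant self-monitoring instruction and to the symptoms in the duration endpoint.
- State that list once and use it to define COVID-19 symptoms in the structured interview and the primary endpoint. The interview can keep its wider coverage of non-respiratory symptoms.
- Reconcile the PUI referral wording in Daily telephone or email follow-up and in section 3a with that list. Leave the study physician's judgement in place. Using the four symptoms as the sole trigger for testing would change a clinical referral rule and could narrow testing for other symptoms.
- Make the change before the pilot data are unblinded.

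The cost is wording in the participant instruction, the interview and the endpoint definitions, plus a few more symptom reports and referrals to testing already planned, some of them negative. The change gives participants a prompt from day 8 onward. It does not alter the contact schedule, so a case first reported at a call after day 14 would still fall outside the window.

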The primary analysis will be comparing the rates of symptomatic, lab-confirmed COVID-19 in all randomized participants using one-sided Fisher's exact test. Intent-to-treat analysis will be used. Secondary endpoints include duration of COVID-19 symptoms without confirmatory test, hospitalization for COVID-19, requiring mechanical ventilation, and mortality. Statistical analysis of the secondary endpoints will be intent-to-treat, using Mann-Whitney test for numerical outcomes and Fisher's test for categorical outcomes. Adverse events and serious adverse events will be compared using Fisher's exact test. Interim analysis will be performed to monitor for futility using a Bayesian criterion. Specifically, an early stopping consideration will be invoked if it is unlikely that poor outcome of hPEP is lower than that of placebo; i.e., its posterior probability is smaller than alpha. The value of alpha will be determined before the first interim analysis.

Go and no-go decision and power consideration

We will plan to move forward to the phase 3 trial if at the end of the pilot phase, the primary analysis has a one-sided p-value less than 0.10. Assuming the placebo rate of COVID-19 outcome is 10.5%, the proposed sample size in the internal pilot will result in an 80% probability of moving forward if the study drug reduces risk by 30% (i.e., from 10.5% to 7.3%).

In addition, the pilot data will be used to re-estimate the sample size in the phase 3 trial, and will be used in the final analysis using adjusted analysis using weighted statistics so as to preserve the overall type I error. Details of sample size re-estimation will be determined before the pilot trial data is unblinded.

3. Study Procedures

a. Procedures

- i. Questionnaires: questionnaires will be performed by telephone by trained research assistants or via web-based questionnaire to support remote administration and immediate data capture.
 1. Screening questionnaire (first call): inclusion and exclusion criteria
 2. Medical history questionnaire (first call): additional questions regarding medications used, number of persons in household
 3. Follow-up questionnaires
 - a. Symptoms (respiratory, non-respiratory)
 - b. Trial medicine adherence
 - c. Psychosocial Behavior (Day7 only)
- ii. Active surveillance for health care utilization and COVID-19 testing at NYP/CUIMC
 1. Participants will be referred for clinical COVID-19 testing if deemed PUI by the study investigator(s)

b. Study Drugs

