e. Protections Against Risks:

- i. In addition to strict exclusion criteria, we will monitor participants for signs/symptoms of potential adverse effects of the study drug by daily follow-up for 7 days. On Day 7, a specific interview concerning acute side-effects of the study medication will be conducted. If any adverse drug effects are suspected based upon symptomatic report, the study physician will determine whether the symptoms are attributable to the study drug. Beyond the two-week period of initial follow-up, we will encourage all participants to reach out to the study coordinator for palpitations, dyspnea on exertion, or visual disturbances occurring up to 30 days after completion of participation. Serious adverse events (SAEs) will be recorded for the full duration of subject participation, however only adverse events of special interest will be recorded upon the Day 7 acute side-effect interview.
- ii. To mitigate risks of COVID-19 among participants, all participants will receive counseling and information regarding current CDC guidelines for exposed household contacts of COVID-19 patients (e.g., decontamination of surfaces, avoidance of unprotected contacts with the index case).

f. Potential Benefits: if the study drug is effective, those randomized to the study drug may benefit from improved COVID-19 outcomes. If benefit is demonstrated, participants randomized to the control arm will have the opportunity to obtain the study drug after study completion. The societal benefits are potentially large.

g. Alternatives: non-participation. Data Safety and Monitoring Plan: A local Data and Safety Monitoring Committee (DSMC) has been established, with [name] (rheumatology) as Chairman of the committee. In addition, the committee will consist of two other members, a pharmacist (TBD) and a statistician ([name]). The DSMC will meet to review all safety data from the patients after the first 100 randomized patients completing their 2-week follow-up, and every 400 randomized patients thereafter. The unblinded statistician will prepare the data for DSMC's review. Each meeting will consist of an open session that includes the study investigators, and a closed session with only the unblinded statistician and the DSMC members.

References

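### The plan does not say whether COVID-19 hospitalizations, ventilation and deaths count in the SAE comparison; if they do, the comparison is less sensitive to drug-caused harm, and no comparison of the other SAEs is planned

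*Combined protocol and SAP*

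**What the plan says.** Section 2, under the additional notes on statistical design and analysis, gives the safety analysis in one sentence: "Adverse events and serious adverse events will be compared using Fisher's exact test". It states no grouping of events, no sidedness and no significance level.

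Section 3.e (Protections Against Risks) sets the collection window: "Serious adverse events (SAEs) will be recorded for the full duration of subject participation". For other events, "only adverse events of special interest will be recorded upon the Day 7 acute side-effect interview". Where a drug effect is suspected from reported symptoms, "the study physician will determine whether the symptoms are attributable to the study drug". That judgement is not linked to any between-arm analysis.

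The list of secondary endpoints in Section 2 includes "Hospitalization for COVID-19", "Mechanical ventilation for COVID-19" and "Mortality attributed to COVID-19". These are analysed by intention to treat, "using Mann-Whitney test for numerical outcomes and Fisher's test for categorical outcomes".

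The protocol does not define an SAE, exempt COVID-19 endpoint events from SAE recording, or plan a comparison of SAEs without them.

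**The concern.** A hospital admission, ventilation or death is serious in the ordinary sense whatever its cause. With no exemption in the collection rule, the natural reading is that COVID-19 admissions and deaths are recorded as SAEs and enter the SAE comparison. Two things follow.

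- **Noise.** COVID-19 admissions unrelated to study drug enlarge both arms' counts and make a given excess harder to see, even if the drug does nothing.
- **Partial offset.** If the drug prevents COVID-19, admissions for it fall on drug while drug-caused serious events rise. Within one count the two move in opposite directions.

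Section 1 names QT prolongation, with its arrhythmia risk, as the major short-term toxicity. An admission for arrhythmia is not a hospitalization for COVID-19, so the SAE comparison is the only planned serious-event comparison that would include it. That comparison matters most when the drug looks effective, because the rule for moving to phase 3 rests on the primary p-value alone. The offset arises in that same situation.

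**Working it through.** **The plan's own figure.** The documents give no SAE rate and no power for safety, so there is no safety figure to reproduce. The efficacy figure, which uses the same arm size and attack rates, does reproduce. The one-sided Fisher test at 0.10, with 800 per arm and 10.5% against 7.35%, has exact power 80.2%, against the stated 80%. It is not in dispute.

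**Inputs from the documents.** n = 800 per arm. Attack rate 10.5% on placebo. A 30% reduction gives 0.105 × 0.70 = 0.0735 on drug.

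**Assumed inputs, not in the documents.**
- Background non-COVID SAE rate b = 0.5% in each arm.
- Drug-caused excess t = 1.5 points, with 0.5, 1 and 2 points as a range.
- Share h of COVID-19 cases that become an SAE through hospitalization = 5%, 10% or 20%. Ventilation and death are taken to occur within these.
- Two-sided Fisher test at 5%, counting only rejections with more events on drug.

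**Formulas.**
- Non-COVID SAEs alone: placebo b; drug b + t.
- Pooled, no benefit: placebo 0.105h + b; drug 0.105h + b + t.
- Pooled, planned benefit: placebo 0.105h + b; drug 0.0735h + b + t.
- Share of the excess cancelled by benefit: (0.105 − 0.0735)h / t = 0.0315h / t.

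**Expected counts at t = 1.5 points.**
- Non-COVID alone: 800 × 0.005 = 4 on placebo; 800 × 0.020 = 16 on drug.
- Pooled with benefit, h = 20%: placebo 800 × (0.0210 + 0.005) = 20.8; drug 800 × (0.0147 + 0.020) = 27.8. The difference falls from 12 to about 7 on a larger total.

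**Power at t = 1.5 points, by exact enumeration.** Non-COVID SAEs alone: 73%.

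| h | Pooled, no benefit | Pooled, planned benefit | Excess cancelled |
|---|---|---|---|
| 5% | 56% | 47% | 10.5% |
| 10% | 45% | 31% | 21% |
| 20% | 34% | 14% | 42% |

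**Splitting the loss.** At h = 10%, power falls by 73 − 45 = 28 points from noise and by a further 45 − 31 = 14 points from the offset. Noise is 28/42, about two-thirds of the loss, and the share is similar at the other two values of h.

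**Other values of the excess, with planned benefit.**

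| t | Non-COVID alone | Pooled, h = 5 / 10 / 20% |
|---|---|---|
| 0.5 points | 13% | 6 / 3 / 1% |
| 1 point | 43% | 22 / 13 / 5% |
| 2 points | 91% | 72 / 54 / 29% |

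The benefit cancels the whole excess only in the corner of this grid with t = 0.5 points and h = 20%, where 0.0315 × 0.20 / 0.005 = 1.26.

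**The case against.** A reader might infer that SAEs are compared as a single total, that COVID-19 events are not separated anywhere, and that any drug benefit therefore hides the drug's own toxicity. The documents do not support that reading.

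- **One total.** The text is silent on grouping. The plural would also fit a comparison by type of event.
- **No separation.** COVID-19 hospitalization, ventilation and mortality have their own tests. A fall in them would be reported beside the SAE result, where a careful reader could suspect an offset.
- **Any benefit hides harm.** In most of the range examined the offset is partial, and most of the lost power is noise that arises without any benefit.
- **Other routes to a signal.** There are daily contacts for seven days, a Day 7 side-effect interview, physician attribution and DSMC review of all safety data.
- **Assumed rates.** Excesses of 1 to 2 points on a 0.5% background triple to quintuple the SAE rate, after exclusions aimed at arrhythmia risk. For a doubling (0.5 points), the separate comparison has only 13% power.
- **No decision role.** The SAE comparison does not enter the phase 3 rule.

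These points limit the claim but do not remove it. The secondary-endpoint tests describe COVID-19 events and leave the other SAEs untested. Events of special interest are recorded at Day 7, although follow-up runs to Day 30. Attribution feeds no analysis, and the content of the DSMC tables is not itemised. None of these routes specifies a comparison of non-COVID SAEs.

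**Conclusion.** The concern holds as an unspecified analysis with a better alternative available. The plan neither defines an SAE nor says whether COVID-19 endpoint events count as one. If they count, as the ordinary meaning of serious implies, the SAE comparison becomes less sensitive to drug-caused harm, through added noise and, if the drug works, a partial offset. Under the central assumptions (0.5% background, 1.5-point excess, 5% to 20% of cases hospitalized), power falls from 73% to between 56% and 34% with no benefit, and to between 47% and 14% with the planned benefit. Every SAE and hospitalization rate here is assumed. The direction does not depend on the exact values, but the size does, and for a small excess neither comparison is likely to detect harm. The primary analysis, the sample size and the efficacy power are unaffected. This should be corrected, but it does not invalidate the design.

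**What to change.** In the additional notes on statistical design and analysis:

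1. Define an SAE, and state whether COVID-19 hospitalization, ventilation and death are counted as SAEs.
2. Add a between-arm comparison of SAEs excluding those three events, and report it beside the comparison of all SAEs.
3. Have each event classified as COVID-19 or not before unblinding.
4. Give the risk difference with an exact 95% confidence interval for both comparisons. With so few events, the interval says more than the p-value.
5. Use the same split in the tables prepared for the DSMC.

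The cost is a few sentences and one extra table. The secondary endpoints already require COVID-19 admissions, ventilation and deaths to be identified. The downside is reliance on blinded attribution, which can fail: shortness of breath is a COVID-19 symptom, and breathlessness on exertion is among the complaints participants are asked to report for safety. Keeping the all-SAE comparison alongside guards against a drug-caused event being classified as COVID-19 and lost from view. The change concerns analysis and reporting only.

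### Does the 80% go probability, shown only at a 10.5% placebo rate, call for a larger or adjustable pilot?

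*Combined protocol and SAP*

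**What the plan says.** Under Go and no-go decision and power consideration (section 2), the trial moves to phase 3 if the pilot's primary analysis gives a one-sided p-value below 0.10. The power statement there reads "Assuming the placebo rate of COVID-19 outcome is 10.5%, the proposed sample size in the internal pilot will result in an 80% probability" of proceeding when risk falls by 30%. Section 1 repeats the same single case.

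The placebo rate is sourced under Control outcome, as a CDC estimate: "symptomatic secondary attack rate of 10.5% (95% CI = 2.9%–31.4%) among household members of COVID-19 patients". The primary analysis is a one-sided Fisher's exact test "comparing the rates of symptomatic, lab-confirmed COVID-19 in all randomized participants". The participants include household contacts of confirmed index cases and of index cases who "are defined as suspected cases, or persons under investigations (PUI), by the treating physician" (Inclusion criteria).

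Three statements describe what may be adapted or monitored:

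- On sample size: "the pilot data will be used to re-estimate the sample size in the phase 3 trial". The pilot data also enter the final analysis through weighted statistics.
- In the Design list: "Phase 2/3 internal pilot, with interim monitoring for futility and safety during the pilot phase".
- In the Data Safety and Monitoring Plan (section 3.g), the committee meets to "review all safety data from the patients after the first 100 randomized patients completing their 2-week follow-up, and every 400 randomized patients thereafter".

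**The concern.** A binary decision to continue or abandon the programme rests on a power figure given at one placebo rate, and the sponsor's own interval for that rate is 28.5 percentage points wide. If the true rate is lower, a drug with exactly the targeted effect is dropped more often than the advertised one time in five. Re-estimation comes only after a go, so it offers no protection here.

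It is also uncertain how well the rate carries over. It describes household members of COVID-19 patients, and the title of the cited source refers to confirmed cases, whereas contacts of merely suspected index cases are enrolled and analysed too. At stake is the chance of discarding an effective prophylactic because events were scarce.

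**Working it through.** **Inputs.** 800 per arm, one-sided 0.10, 30% relative reduction and placebo rate 10.5% with 95% CI 2.9% to 31.4% (Statistics: Control outcome, Effect size, Design). Fisher's exact test on all randomised participants (Additional notes on statistical design and analysis). Go if p < 0.10.

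**1. The stated 80%.** The treated rate is 0.7 × 10.5% = 7.35%, which the document rounds to 7.3% in one place and 7.4% in another. The go probability is the sum, over all pairs of event counts, of Bin(x_P; 800, p_P) × Bin(x_H; 800, p_H), keeping only pairs whose one-sided Fisher p is below 0.10.

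- 10.5% vs 7.35%: 80.2%
- 10.5% vs 7.3%: 81.2%
- 10.5% vs 7.4%: 79.1%

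The sample size formula agrees. With mean rate 0.08925 and difference d = 0.0315:

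n = [1.2816 × √(2 × 0.08925 × 0.91075) + 0.8416 × √(0.105 × 0.895 + 0.0735 × 0.9265)]² / 0.0315² = 0.7320 / 0.000992 ≈ 738.

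Continuity correction: (738/4) × [1 + √(1 + 4/(738 × 0.0315))]² ≈ 800 per arm. The plan's figure is reproduced.

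**2. Other placebo rates.** Same test, 800 per arm, treated rate = 0.7 × placebo rate. Expected events = 800 × 1.7 × placebo rate.

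| Placebo rate | Expected events, both arms | Go probability | n per arm for 80% |
|---|---|---|---|
| 2.9% (CI limit) | 39 | 37.6% | 3,089* |
| 5% | 68 | 53.5% | 1,750 |
| 7% | 95 | 65.5% | 1,250 |
| 8% | 109 | 70.4% | 1,075 |
| 9% | 122 | 74.7% | 950 |
| 10.5% | 143 | 80.2% | 800 |
| 12% | 163 | 84.7% | 700 |
| 15% | 204 | 91.2% | 550 |
| 31.4% (CI limit) | 427 | 99.8% | 219* |

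*Continuity-corrected formula; the other sizes are from exact enumeration in steps of 25.

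Exact type I error of the pilot test is 0.087 at a 10.5% null rate and 0.085 at 8%, below 0.10 in both cases.

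**3. What is visible during the pilot.** The futility criterion is the posterior probability that the poor-outcome rate on hydroxychloroquine is below that on placebo. It cannot be computed without event counts by arm, and adding the two counts gives the pooled rate. An unblinded statistician prepares the committee's data. The event rate will therefore be known inside the pilot, although no rule says what to do if it is low. At a pooled rate of 8.925%, 1.96 × √(0.08925 × 0.91075 / N) is 2.5 points at N = 500 and 1.9 points at N = 900.

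**4. The price of acting on a low rate.** Take an illustrative blinded rule: re-size at 900 participants from the pooled rate, with a floor of 800 and a cap of 1,200 per arm. Simulation gives:

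| Placebo rate | Go, fixed 800 per arm | Go, with extension | Mean n per arm |
|---|---|---|---|
| 5% | 53.5% | 67% | 1,200 |
| 7% | 65.5% | 78% | 1,157 |
| 8% | 70.4% | 80% | 1,069 |
| 10.5% | 80.2% | 82% | 843 |

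The cap adds up to 2 × 400 = 800 participants, which is 50% of 1,600. When 10.5% is exactly right, 800 per arm is also exactly the required size, so sampling noise alone triggers an extension in about 51% of trials, for a gain of about 2 points.

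**The case for a change.** The best case for a change does not need the extreme 2.9%. At 8%, well inside the printed interval, a drug with the targeted effect is dropped 30% of the time rather than 20%; at 5%, 46%. The learning that a pilot provides is applied only to phase 3, after the decision it might have informed. A table of go probabilities and a pooled event count at reviews already scheduled would need no extra enrolment.

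The arithmetic stands, and so does the observation that re-estimation comes after the go decision. Other parts are weaker:

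- The monitoring does expose event counts, through the futility analysis. What is absent is only an action rule.
- A rate above 10.5% does not make the pilot wasteful, because its participants count in the final phase 3 analysis. Most of the printed interval lies above 10.5%, where the go probability exceeds 80%.
- A no-go can be read without the power at the observed rate. A confidence interval for the treatment effect, which analysts would ordinarily report, shows whether a 30% reduction is still compatible with the data.
- The point about suspected index cases has no direction or size in the documents. The screening step ("Screening questionnaire (first call): inclusion and exclusion criteria") should already record which index criterion was met. The case report forms are not available, so it cannot be said that a later test result goes uncollected.

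The table and the pooled count are good reporting, but neither changes the sample size, the test or the decision.

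**Conclusion.** No change is needed. The 80% is correct under an assumption that the plan states as such, with its confidence interval printed. Powering on a disclosed point estimate is ordinary practice, and the all-randomised comparison and the 0.10 error rate hold whatever the placebo rate turns out to be.

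The sensitivity is worth knowing: about 54% at 5%, 70% at 8%, 85% at 12% and 91% at 15%, with 38% and 99.8% at the CI limits. The documents do not show on which side of 10.5% the true rate lies. Raising the go probability at low rates means enrolling more people, up to 50% more in the illustrated version, which still reaches only 67% at a 5% rate. Keeping the pilot at a fixed 1,600 is a fair trade-off. If the sponsor wishes, it can print the go probability over several placebo rates and report the pooled event rate and an effect interval beside the go/no-go result. These are optional additions.

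The figures assume a constant 30% relative reduction, independent participants, complete outcome data and no futility stop. The simulated extension also assumes completed outcomes for all 900 participants at the re-sizing look. The section 3.g schedule implies reviews at 100, 500, 900 and 1,300 only if the later ones are counted on from the first; if they are triggered by randomisation, somewhat fewer outcomes would be complete.
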